8.1.3. Analysis Visits and Visit Windowing

In general, all scheduled visits will be used as analysis visit for descriptive analysis tables and listings.

If a scheduled visit is missing, an unscheduled visit may be mapped to take its place if and only if it is within the visit window of the missing scheduled visit. The following table describes the visit mapping of unscheduled post-baseline visits in the event that a scheduled visit is missing. If there are multiple unscheduled visits, the closest one to the projected date will be selected; if there are ties, the later measurement will be used.

| Parameter | Analysis Visit/Time Point Window |
|-------------------------|--|
| Labs | Study Day ± 3 days from Target Day Early termination (ET) visits are mapped to the nearest missing analysis visit, using the same window, after unscheduled visits are considered. |
| MRI | Day 85: Study Day ≥ 78 ; ET visits with Study Day ≥ 65 will be mapped to Day 85. Day 141: Study Day ≥ 113 |
| Histology Endpoints | Day 141: Any post-baseline |
| Fibroscan | Day 141: Any post-baseline |
| Vital Signs | Study Day ± 3 days from Target Day; ET visits are mapped to the nearest missing analysis visit, using the same window, after unscheduled visits are considered. |
| Anthropometric Measures | Study Day ± 3 days from Target Day (For body weight) Study Day ± 14 days from Target Day (For waist-hip ratio related parameters) ET visits are mapped to the nearest missing analysis visit, using the same window, after unscheduled visits are considered |
| ECG | Study Day ± 3 days from Target Day ; ET visits are mapped to the nearest missing analysis visit after unscheduled visits are considered using Study Day |
| PK | Depending on the time point, the window for each time point is specified in the PK sampling schedule. If multiple unscheduled records are available, the sample collected closest to the nominal time will be selected. If the distance is the same, the later one will be selected. |

Measurements from all protocol planned visits will be summarized in descriptive tables and figures. For PD endpoints that are analyzed using MMRM analysis, only measurements taken at

analysis visits (e.g., Day 1, Day 8, 15, 29, 57, etc.) will be included in the analysis and corresponding data presentation. Analyses will utilize the measurements taken at the scheduled visits or the unscheduled visit that have been mapped to a scheduled visits, as described in [Section 8.1.3](#). If there are duplicate results from the same sample are available, e.g., with the identical sampling date and time, the average value will be used for data analysis and both raw data and average value will be listed.

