Measurements from all protocol planned visits will be summarized in descriptive tables and figures. For pharmacodynamic endpoints that are analyzed using MMRM analysis, only measurements taken at weekly analysis visits (eg, Day 1, Day 8, 15, 22, 29, 36, etc) will be included in the analysis and corresponding data presentation. Analyses will utilize the measurements taken at the scheduled visits whenever they are available. If not available, the analysis will use the measurement mapped to that scheduled visit (whichever is the closest to the target date, and if there are two measurement before and after the target day with same duration, use the measurement taken at the later day) If there are duplicate results from the same sample are available, eg, with the identical sampling date and time, the average value will be used for data analysis and both raw data and average value will be listed. EOS/ET visits will be summarized in descriptive summary. ET visits will be eligible to be mapped to missing protocol planned visits, but will not on its own be considered an analysis visit or time point.

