8.1. General Considerations

In general, scheduled visits from baseline to Day 162 will be summarized. For summaries of worst post-baseline or post-baseline min/max, all visits will be considered, including unscheduled.

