All ambulatory clinic visits will have a study window of ± 1 day. Window for MRI-PDFF will be ± 7 days. The first liver biopsy will be done during the screening period. The second liver biopsy will be performed within 14 days after the last dose of study intervention. Liver biopsies (first and second) will be done after MRI-PDFF.

- a. For any subject who withdraws before completion of the study, an Early Termination (ET) visit will be conducted, if possible; with the same assessments as the Day 141 visit.
- b. A liver biopsy with NASH that meets study inclusion criteria, performed within 24 weeks from baseline visit with the sample deemed interpretable by the central reader is acceptable instead of the baseline liver biopsy. A second liver biopsy will be done within 14 days of the last dose of study intervention. Liver biopsies (first and second) will be done after MRI-PDFF. If out of a window, a liver biopsy should still be performed as close to the target date as possible, but a protocol deviation should be recorded.
- c. Complete physical exam done at screening to include recording height, weight, and calculating BMI.
- d. Physical examinations will be performed if clinically indicated.
- e. Fibroscan should be performed during screening, prior to magnetic resonance imaging (MRI) for all subjects. Fibroscan will be repeated on D141/ET.
- f. 12-lead safety ECGs will be recorded as single bedside measurements. Additional ECG may be conducted if clinically indicated.
- g. On Day 1, urine drug screen can be done at a local laboratory.
- h. Clinical laboratory tests (performed under fasting conditions, ≥ 10 hours) will include biochemistry, hematology, and coagulation, and FSH for determination of post-menopausal status. For all subjects, alanine transaminase (ALT) and aspartate transaminase (AST) will be collected twice during the Screening period (at least 2 weeks apart), with the 2nd assessment to be collected at Day -7 to Day -3. A 3rd assessment, if required, will be collected via unscheduled visit (refer to Exclusion criterion 3).
- i. Serology tests will include Hepatitis B surface antigen, Hepatitis C Virus, and Human Immunodeficiency Virus (HIV) 1 and 2 antibodies.

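### Part 2 keeps Part 1's ±3-day window for labs, vital signs and weight although its analysis visits appear to be about four weeks apart after Day 29, so most early-termination values fit no visit

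*SAP*

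**What the plan says.** All references are to the Part 2 SAP unless stated.

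- **Mapping rule (8.1.3).** Labs have a ±3-day window, and "Early termination (ET) visits are mapped to the nearest missing analysis visit, using the same window, after unscheduled visits are considered". Vital signs have the same structure: ± "3 days from Target Day; ET visits are mapped to the nearest missing analysis visit, using the same window". Body weight also has ±3 days and the same ET rule.
- **What enters the models (8.1.3).** For PD endpoints analysed by MMRM, only measurements at "analysis visits (e.g., Day 1, Day 8, 15, 29, 57, etc.) will be included in the analysis".
- **What enters the tables (8.1).** In general, "scheduled visits from baseline to Day 162 will be summarized". The next sentence there lets worst-value and min/max summaries use all visits, including unscheduled ones.
- **What is collected at ET (12.1, footnote a).** For a subject who withdraws, "an Early Termination (ET) visit will be conducted, if possible; with the same assessments as the Day 141 visit".
- **Other rows of the window table (8.1.3).** Waist-hip measures have ±14 days. Histology and Fibroscan accept any post-baseline value. MRI sends an ET visit from Day 65 onwards to Day 85. The ECG row says only that "ET visits are mapped to the nearest missing analysis visit after unscheduled visits are considered using Study Day" and does not repeat the window limit.
- **Part 1 SAP (9.1.3).** The ±3-day rule is the same, but its analysis visits are weekly. It adds that "EOS/ET visits will be summarized in descriptive summary", and that an ET visit is not an analysis visit in its own right. Neither statement is carried into Part 2.

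**The concern.** The ±3-day width fits a weekly schedule. In Part 2 the rule looks carried over: the MRI row was rewritten for the new schedule, while labs, vital signs and weight were left as they were. With visits 28 days apart, each window takes up 7 days of the cycle, and an ET visit in the other 21 has nowhere to go.

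Take a subject who leaves on Day 70. Labs, weight and vital signs are all measured, but Day 70 is 13 days after Day 57 and 15 days before Day 85, so none of the values maps to a visit.

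The values at risk are the last ones from subjects who leave, in a single open-label arm of about 20. Some may have left because of a laboratory finding. The lab change and shift tables in 8.5.2 are by visit, and that section specifies no worst-post-baseline lab table through which an unmapped value could return.

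**Working it through.** The documents give no coverage figure for these windows, so there is none to reproduce. The check is a count of days.

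**Inputs**
- Analysis visits on Days 8, 15, 29 and 57 (8.1.3), and lipid analyses at Days 85 and 113 (8.4.3.1).
- Follow-up visits on Days 141 and 162 (Protocol 4.2).
- Home visits between clinic visits are for dosing; evaluations take place at clinic visits (Protocol 4.2).
- Window: |ET day − target day| ≤ 3.

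Every ET day has equal weight. Days 30 to 140 make 140 − 30 + 1 = 111 days.

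| Target | Days in window, within 30–140 | (a) Window width only | (b) Only a visit on or after the ET day can be missing |
|---|---|---|---|
| 29 | 30–32 | 3 | 0 |
| 57 | 54–60 | 7 | 4 |
| 85 | 82–88 | 7 | 4 |
| 113 | 110–116 | 7 | 4 |
| 141 | 138–140 | 3 | 3 |
| Total | | 27 | 15 |

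- (a) Unmapped: 1 − 27/111 = 75.7%.
- (b) Unmapped: 1 − 15/111 = 86.5%.

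Column (b) matters because the rule maps only to a *missing* visit, and a subject who terminates has usually attended the visit before.

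**Whole period, Days 2–140 (139 days).** The windows of Days 8, 15 and 29 now count in full. (a) covers 6 × 7 + 3 = 45 days, so 1 − 45/139 = 67.6% are unmapped. (b) covers 6 × 4 + 3 = 27 days, so 1 − 27/139 = 80.6% are unmapped.

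**Part 1 comparison.** Weekly visits with ±3 days cover 7 of 7 days, so none is unmapped on width. Under the missing-visit condition, 4 of 7 days map and 3/7 = 43% do not.

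**Sensitivity to the redacted schedule.** Suppose there were also visits on Days 71, 99 and 127. For Days 30–140, (a) becomes 1 − (27 + 21)/111 = 56.8% and (b) becomes 1 − (15 + 12)/111 = 75.7%.

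**Subjects affected.** Expected drop-out is redacted. If 1 to 4 of 20 subjects left after Day 29, the number whose ET value is unmapped runs from 1 × 0.757 = 0.76 to 4 × 0.865 = 3.46.

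**Would ±14 days alone be enough?** Under (a), all 111 days are covered. Under (b), the windows cover 15 + 15 + 15 + 14 = 59 days, leaving 1 − 59/111 = 46.8% unmapped.

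**The case against.** The strongest reply is that little is lost. Most of its parts stand and limit the point.

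- **A reader might infer that an abnormal ET lab value would appear only in a listing.** The documents do not support that. The DILI summary (8.4.3.3) takes the maximum ALT or AST over all visits for subjects with normal baseline, and an eDISH plot is planned. Vital-sign threshold counts (8.5.4) use all post-baseline visits. Clinically significant lab findings are recorded as adverse events (Protocol 7.2.5 and Appendix 3) and so reach the TEAE tables. The gap remains for most other labs. For subjects with raised baseline ALT or AST, 8.4.3.3 states no all-visits rule.
- **A reader might infer that the PD estimates rest on completers.** They do not. Early leavers keep every attended visit in the MMRM; only the last value is missing.
- **A reader might infer that every Part 1 ET visit found a slot.** Part 1 has the same missing-visit condition, so the contrast is one of window width.
- **Stopping drug is not leaving the study.** Protocol 6.1 keeps subjects who discontinue treatment under observation, so later scheduled visits may supply data. The loss falls mainly on subjects who withdraw and attend an ET visit.
- **Part 2 does not say that ET values are excluded from descriptive tables.** It dropped Part 1's sentence including them and also the one denying ET the status of an analysis visit. It summarises all planned visits, and footnote e of the schedule refers to D141/ET. One could read ET as a planned visit, but the SAP does not say so.

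The inferred schedule is a fair caveat. The sensitivity count shows that the gap survives a denser schedule.

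**Conclusion.** The point holds, but it is narrow. After Day 29, the ±3-day window leaves about 76% of possible ET dates without a visit on width alone, and about 86% if earlier visits were attended. Over Days 2–140 the width-only figure is about 68%. For subjects who leave and attend an ET visit, the last lab and weight values drop out of the MMRM. With vital signs, they also drop out of the by-visit tables, unless ET is read as a planned visit.

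The percentages assume evenly spread ET dates and a four-weekly schedule inferred around redactions. The count of about 0.8 to 3.5 subjects also rests on an assumed 1 to 4 early leavers. The primary histology endpoint and the MRI analysis have their own wide windows and are not touched. The change is worth making because the data are already collected and the remedy is cheap, not because the estimates would move far.

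**What to change.** 1. In 8.5.2, add a worst-post-baseline lab shift table that includes ET and unscheduled values. It recovers the safety information whatever the windows are.
2. In 8.1.3, give labs, vital signs and body weight a Part 2-specific window, for example ±14 days as already used for waist-hip measures. Let an ET value map forward to the next missing scheduled visit for that parameter within it.
3. Show ET values that still do not map in a last-on-treatment/ET row of the by-visit tables. This row is needed: with ±14 days and earlier visits attended, 46.8% of dates from Day 30 to Day 140 remain unmapped. Day 70 is among them, being 15 days before Day 85.

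Windows that meet midway between visits, but still map only to the nearest missing visit, would not be enough. Day 70 would fall in the Day 57 window, and Day 57 would normally have been attended.

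The cost is SAP wording and programming, with no new data. The drawback is that some mapped values lie up to about 14 days from their target day; flag these in the listing.

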4.2.2. Rationale for Part 2 Study Population

BIO89-100 is being developed for NASH with fibrosis. Preliminary data from Part 1 demonstrated favorable safety and tolerability and robust, clinically meaningful reductions in liver fat assessed by MRI-PDFF and in ALT, with reductions in both measures beyond thresholds that have been associated with histological benefit in patients with NASH, with repeated dosing of BIO89-100 for 12 weeks, in a similar population to the intended population in Part 2. Part 2 extends the study to subjects with biopsy-proven NASH and fibrosis (NAS ≥ 4 , fibrosis stage F1 with high risk, F2 or F3). This population of patients meets current regulatory expectations for patients to be enrolled in later stage studies for NASH, and will allow to assess changes in liver histology, as well as changes in liver fat as measured by MRI-PDFF and other biomarkers in a population of patients aligned with NASH registration studies. Histological endpoints will include at least a 2-point improvement in NAS with at least a 1-point improvement in ballooning or lobular inflammation with no worsening of fibrosis (primary), improvement of fibrosis by at least 1 stage without worsening of NASH, and NASH resolution without worsening of fibrosis (secondary), and additional exploratory endpoints. In addition to other exploratory histological endpoints, exploratory analysis of histological endpoints in the subset of MRI-PDFF responders ($\geq 30\%$ relative reduction in liver fat by MRI-PDFF at D85) will be conducted. The study population is appropriate for assessment of these and other PD endpoints.

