9.1.3. Analysis Visits and Visit Windowing

In general, all scheduled visits will be used as analysis visit for descriptive analysis tables and listings.

If a scheduled visit is missing, an unscheduled visit may be mapped to take its place if and only if it is within the visit window of the missing scheduled visit. The following table describes the visit mapping of unscheduled post-baseline visits in the event that a scheduled visit is missing. If there are multiple unscheduled visits, the closest one to the projected date will be selected; if there are ties, the later measurement will be used.

| Parameter | Analysis Visit/Time Point Window |
|--------------------------|---|
| Labs | Study Day \pm 3 days from Target Day ET visits are mapped to the nearest missing analysis visit, using the same window, after unscheduled visits are considered. |
| MRI; Fibroscan | Day 50: $36 \leq$ Study Day ≤ 64 (± 14 Days); Day 92: Study Day ≥ 78 ; ET visits within Study Day < 65 will be mapped to Day 50; ET visits with Study Day ≥ 65 will be mapped to Day 92. |
| Vital Signs | Study Day \pm 3 days from Target Day; ET visits are mapped to the nearest missing analysis visit, using the same window, after unscheduled visits are considered. |
| Anthropomorphic Measures | Study Day \pm 3 days from Target Day (For body weight) Study Day \pm 14 days from Target Day (For waist-hip ratio related parameters) ET visits are mapped to the nearest missing analysis visit, using the same window, after unscheduled visits are considered |
| ECG | Study Day \pm 3 days from Target Day ; ET visits are mapped to the nearest missing analysis visit after unscheduled visits are considered using Study Day |
| PK | Depending on the time point, the window for each time point is specified in the PK sampling schedule. If multiple unscheduled records are available, the sample collected closest to the nominal time will be selected. If the distance is the same, the later one will be selected. (Actual time should be used for PK analysis) |

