- j. Serum urine pregnancy test will be conducted at screening; at all other timepoints urine pregnancy test will be done to guide clinical decisions to dose on dosing days. On dosing days in the clinic, a urine pregnancy test will be obtained locally; in addition, a urine sample will be sent to the central lab. If urine test is positive, a confirmatory serum pregnancy test will be conducted.
- k. Vital signs include blood pressure, pulse, body temperature, and respiratory rate; vital signs will be measured pre-dose (prior to scheduled blood draws and study intervention administration. Blood pressure and pulse will be measured in duplicate, the first measurement will be taken up to 15 minutes before the indicated timepoint. Additional vital signs measurement may be done if clinically indicated. Subjects must be in a supine or semi-erect/seated position and resting for at least 5 minutes prior to measurements.

1. Study intervention will be administered SC to the abdomen region by qualified study personnel or by the subject (under supervision) at ambulatory clinic visit and will be administered at home by the subject at the rest of the planned dosing days. Subjects will be observed for 15 minutes after each dose.
- m. At the designated timepoints, study intervention will be administered at the subject's home. If home administration is not feasible, not desired by the subject, or deemed inappropriate option by the investigator for any reason, in-clinic study intervention administration may take place at some or all of these timepoints.
- n. PK blood samples will be collected at the specified timepoints. Additional blood samples for PK analysis may be collected if clinically indicated (e.g., in case of SAE). For PK sample collection instruction/procedures, refer to the relevant manual.
- o. At Screening, MRI-PDFF to be done within 35 days of baseline (Day 1). On Days 85 and 141, MRI-PDFF to be done within ± 7 days of the planned visit date. If out of the window, MRI-PDFF should still be performed as close to the target day as possible, but protocol deviation should be recorded.
- p. Samples for carboxy-terminal collagen crosslinks (CTX), N-terminal propeptide of type 1 collagen (P1NP) and osteocalcin will be obtained at the designated timepoints.
- q. Subjects who test positive for neutralizing antibodies to BIO89-100 at the EOS visit (or at the ET visit if withdrawn from study) [REDACTED]

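### Part 2 SAP: the MRI Day 85 window and its early-termination rule have no upper limit, so a scan taken on Day 113 or later is assigned to Day 85 instead of Day 141

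*SAP*

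**What the plan says.** The MRI row of the window table in SAP Part 2, section 8.1.3, has three rules:

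- "Day 85: Study Day ≥ 78", with no upper limit;
- ET visits from Study Day 65 on "will be mapped to Day 85", again with no upper limit;
- "Day 141: Study Day ≥ 113".

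The text above the table limits when mapping is used: "If a scheduled visit is missing, an unscheduled visit may be mapped to take its place", provided that the unscheduled visit lies inside the window of the missing one. If several unscheduled visits compete for one target, the closest is taken.

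The schedule in SAP Part 2, section 12.1, gives the planned scans: "On Days 85 and 141, MRI-PDFF to be done within" 7 days either side. Footnote a of that schedule gives the ET visit the same assessments as Day 141, and these include MRI-PDFF.

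Section 8.4.4 summarises MRI-PDFF responders at Day 85 and Day 141 from the data observed at each visit. Protocol section 4.2.2 plans an "exploratory analysis of histological endpoints in the subset of MRI-PDFF responders", with response judged at Day 85.

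**The concern.** The two windows overlap, and the ET rule sends late scans to the earlier of the two visits. A subject who stops near the end of treatment has an ET scan that is in substance an end-of-treatment measurement, yet the rule labels it as Week 12.

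Three comparisons suggest that this was not intended:

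- In the same table, labs, vital signs, anthropometric measures and ECG map an ET visit to the nearest missing analysis visit.
- In the same table, any post-baseline biopsy counts as Day 141. An early stopper's biopsy would therefore be analysed at Day 141 and the MRI from the same termination assessments at Day 85.
- The Part 1 SAP (section 9.1.3) closes its earlier window (Day 50 is Study Day 36 to 64) and sends ET scans from Day 65 on to its last MRI visit, Day 92. Part 2 uses the same cut-offs, 78 and 65, but attaches them to the first of its two MRI visits. That looks like an adaptation slip, although this is an inference.

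At stake are the MRI-PDFF change and responder results at both visits, which belong to a secondary endpoint, and possibly membership of the exploratory Day 85 responder subset. Stops this late are foreseen: Protocol Appendix 5 allows an End of Treatment visit in place of a COVID-19 interruption once a Part 2 subject has reached the Day 106 visit.

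**Working it through.** The plan gives no figure to reproduce here. The check applies the three rules to each study day up to Day 162, the end-of-study visit.

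**Inputs.** Windows and ET rule: SAP Part 2, section 8.1.3. Targets: Day 85 and Day 141. Dosing days 1, 8, ..., 134 (20 doses) and planned cohort of 20: SAP Part 2, section 3.1.

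**Overlap.** A day meets both windows if it is at least 78 and at least 113, that is, from Day 113 on. Up to Day 162 this is 162 − 113 + 1 = 50 days.

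**Distance to target.** For a scan on day d, compare |d − 85| with |d − 141|. The midpoint is (85 + 141)/2 = 113, which is also the SAP's own lower limit for Day 141.

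| Scan day | Doses scheduled by then | Days from 85 | Days from 141 | ET rule assigns to |
|---|---|---|---|---|
| 106 | 16 | 21 | 35 | Day 85 |
| 113 | 17 | 28 | 28 | Day 85 |
| 120 | 18 | 35 | 21 | Day 85 |
| 130 | 19 | 45 | 11 | Day 85 |
| 134 | 20 | 49 | 7 | Day 85 |
| 140 | 20 | 55 | 1 | Day 85 |

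Days 113 to 140 are 28 possible ET days. On 27 of them the scan is nearer to Day 141, Day 113 is a tie, and on none is it nearer to Day 85. For ET scans on Days 65 to 112, Day 85 is the nearer target and the assignment is defensible.

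**Literal outcome for an ET scan on Day 113 or later.**

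- Day 85 scan present: the slot is filled, the ET scan is unused, and Day 141 is empty.
- Day 85 scan missing: the ET value is analysed as Day 85 and can place the subject in or out of the Day 85 responder subset, and Day 141 is empty.

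**Size per subject.** Suppose that n subjects are observed at a visit and k respond. Losing one responder changes the rate by k/n − (k − 1)/(n − 1) = (n − k)/[n(n − 1)]. Losing one non-responder changes it by k/(n − 1) − k/n = k/[n(n − 1)]. Each is at most 1/n. With n = 20 the largest shift is 1/20 = 5 percentage points; with n = 18 (assumed for illustration) it is 1/18 = 5.6. Adding one relabelled scan at Day 85 has the same bound, with n counted after the addition.

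**After closing Day 85 at Study Day 112.** Days meeting both windows fall from 50 to 0, and ET scans on Days 113 to 140 go to Day 141.

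**The case against.** The strongest reply is that mapping operates only when a scheduled visit is missing. A subject who stops after Day 113 will normally have the Day 85 scan already, so the missing visit is Day 141. A Day 130 scan meets the Day 141 window, and on that reading nothing is lost. A programmer could take this route. It requires setting aside the one sentence that names ET visits, however, and the SAP does not say which rule prevails. The closest-date rule does not settle it, because it chooses among several scans for one target and not between two windows for one scan. In an open-label cohort the choice should be fixed in the text.

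Other parts of the reply stand and limit the point. Scheduled scans are used directly, so completers are untouched. For an ET scan to be reported as Week 12, the Day 85 scan must be missing and the ET scan must fall on Day 113 or later. The responder subset, which is exploratory, is affected only in that double case.

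A reader might also infer that Part 1 has the same fault and needs the same change. The documents do not support that. Part 1 has no overlap and sends late ET scans forward to Day 92. Its looseness is smaller: an ET scan before Day 65 "will be mapped to Day 50" even if it was taken before Day 36, outside that row's own 36 to 64 window. Holding Part 1 ET scans strictly to the stated windows would discard those from Days 65 to 77, which now count at Day 92. It would also change a rule after Part 1 top-line MRI-PDFF results were available (Protocol section 2.3.3).

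**Conclusion.** Wrong as written, within a narrow scope. The conclusion rests on reading the ET sentence literally, as the only rule addressed to ET visits. It concerns Part 2 ET scans on Day 113 or later; an unscheduled non-ET scan from Day 113 on also falls in both windows, with no rule to separate them.

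Three stronger readings are tempting and not supported. It does not follow that the Day 141 results or the Day 85 responder subset will be biased, because the documents give no ET rate and the number of affected subjects may be zero. Nor is 5 percentage points a fixed effect of each misplaced scan: responder rates use observed data, so it is a ceiling for one subject when all 20 are observed, and slightly higher with fewer. The primary histology result is not at risk, because its own row assigns any post-baseline biopsy to Day 141.

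**What to change.** In the MRI row of SAP Part 2, section 8.1.3:

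- Day 85: Study Day 78 to 112. ET scans on Days 65 to 112 may stay mapped to Day 85.
- Day 141: Study Day 113 or later, stated to include ET scans on Day 113 or later.
- If more than one scan qualifies for a target, take the closest.

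The cost is one table row and no new data. The edit should be made before the Part 2 MRI data are analysed; if that has already happened, report it as a documented deviation and show any affected subject under both assignments.

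Leave the Part 1 rule as it is. At most, note that ET scans before Day 36 are counted at Day 50, and exclude them in a sensitivity analysis if any exist.
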